### COMPLIANCE STATEMENT

The study will be carried out in accordance with Good Clinical Practice (GCP) as required by the United States (US) Code of Federal Regulations (CFR) applicable to clinical studies (45 CFR Part 46, 21 CFR Part 50, 21 CFR Part 56, and 21 CFR Part 312) and ICH E6; 62 Federal Register 25691 (1997).

#### **SYNOPSIS**

#### Title:

A Randomized, Double-Blind, Active-Controlled Study to Assess the Safety and Local Tolerability of DFD-03 (tazarotene) Lotion, 0.1% compared to Tazorac® (tazarotene) Cream, 0.1% in the Topical Treatment of Acne Vulgaris for 12 Weeks

**Sponsor:** [name], Ltd

[name]

Study Centers: 10 Number of Subjects: 150 randomized

**Study Period:** 12 weeks **Clinical Phase:** Phase 2

## **Objective:**

The objectives of this study are to determine the safety and local tolerability of DFD-03 (tazarotene) Lotion 0.1% and to compare it with Tazorac (tazarotene) Cream, 0.1% in the topical treatment of acne vulgaris for 12 weeks.

#### **Methods:**

This will be a multicenter, randomized, double-blind, parallel-group, active-controlled study.

Subjects with mild to moderate facial acne vulgaris will be randomized to treatment with either DFD-03 (tazarotene) Lotion 0.1%, Tazorac (tazarotene) Cream, 0.1%, Vehicle Lotion or Vehicle Cream in a ratio of 2:2:1:1. Upon randomization, the treatment group (DFD-03 group or Tazorac group) will be known but the treatment assignment (active vs. vehicle) within that treatment group will remain blinded. During the 12-week treatment period subjects randomized to DFD-03 Lotion or Vehicle Lotion will use the study drug twice daily with approximately 12 hours between applications. Subjects randomized to Tazorac Cream or Vehicle Cream will use the study drug once daily in the evening. Subjects will be instructed to treat the entire face.

At selected site(s), subjects with acne lesions of any severity on the chest and/or back (including shoulders) may be enrolled provided they have met all inclusion criteria including mild to moderate acne on the face and have not met any exclusion criteria and will treat all areas affected with acne on the face, chest and/or back, including shoulders, if applicable. Up to 12 subjects with acne involvement on the face, chest and/or back including shoulders will be randomized to treatment with either DFD-03 (tazarotene) Lotion 0.1%, Tazorac (tazarotene) Cream, 0.1%, Vehicle Lotion or Vehicle Cream in a ratio of 2:2:1:1.

At selected site(s), subjects who are 9 to 11 years of age will be randomized to DFD-03 group only in a 1:1 ratio of DFD-03 (tazarotene) Lotion 0.1% to Vehicle Lotion. Approximately 8 subjects will be enrolled in this age range and the inclusion criteria on the number of inflammatory and non-inflammatory lesions will not be applicable to these subjects.

Safety assessments will include the investigator's assessment of local cutaneous tolerance/application site reactions on the face (dryness, non-lesional erythema, peeling, stinging, burning, and itching), vital signs (blood pressure and pulse rate), and adverse events (AEs). Local cutaneous tolerance reactions on the chest and/or back including shoulders (if applicable), will be assessed separately. Urine pregnancy tests will be performed at Screening, Baseline and at every visit through Week 12 for all female subjects. A physical examination will be performed at the Baseline and at the End of Study Visit.

The Cardiff Acne Disability Index (CADI) will be used to assess the quality of life in all subjects at Baseline (Day 1) and at Weeks 4, 8 and 12.

The investigator will assess efficacy by using an Investigator's Global Assessment scale (IGA 5-point scale) and by counting the number of inflammatory and non-inflammatory lesions on the face at Baseline and Weeks 4, 8, and 12.

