# 7.5.1 Investigator's Global Assessment (IGA) of the Face

The IGA scale to be used in the study is a measure of static evaluation of qualitative overall acne severity. IGA is an ordinal scale with five severity grades (reported only in integers, e.g., 0 to 4). Each grade is defined by a distinct and clinically relevant morphologic description to minimize inter-observer variability (Table 4). The grades on the scale have been sufficiently defined to appropriately and unambiguously represent each severity grade on the scale. The investigator is required to perform IGA scoring at each visit. The IGA should always be done prior to lesion counts.

Grade	Description
0	Clear skin with no inflammatory or non-inflammatory lesions
1	Almost clear; rare non-inflammatory lesions with no more than rare papules
2	Mild severity; some non-inflammatory lesions with no more than a few inflammatory lesions (papules/pustules only, no nodular lesions)
3	Moderate severity; up to many non-inflammatory lesions and may have some inflammatory lesions, but no more than one small nodular lesion
4	Severe; up to many non-inflammatory and inflammatory lesions, but no more than a few nodular lesions

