## 7.5.4 Cardiff Acne Disability Index (CADI)

The CADI is a short 5 item questionnaire that will be conducted by all subjects at Baseline, Week 4, 8, and 12. The questionnaire rapidly assesses the disability caused by the acne. It consists of 5 questions. The scoring for each question is done from 0 to 3 (a=3, b=2, c=1, d=0). The CADI score is calculated by summing the score of each question resulting in a possible maximum of 15 and a minimum of 0. The higher the score, the more the quality of life is impaired.

The CADI questionnaire is provided in Appendix 2.

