### 7. Conduct clinical assessments:

- a. IGA for the face (Table 4). IGA assessments should always be done prior to lesion counts.
- b. Count inflammatory and non-inflammatory lesions on the face and, if applicable, on chest and/or back (including shoulders) for selected site(s). These counts should be recorded separately for the face and, if applicable, chest and/or back (including shoulders) for selected site(s).
- c. Local cutaneous safety evaluation for dryness, non-lesional erythema, and peeling. The investigator should also ask the subject if any burning, stinging, or itching has occurred on the face in the last 14 days. These evaluations should be recorded separately for the face and, if applicable, chest and/or back (including shoulders) for selected site(s).
- 8. Administer the CADI questionnaire.
- 9. The independent third party study medication dispenser will perform the following procedures:
  - a) Assign a subject number using the subject kit #. Randomize subject by using the lowest available number of study kit at the study site.
  - b) Weigh and then dispense 2 bottles or 1 tube of study product (depending on the treatment assignment) to subjects. For the selected site(s) who will enroll subjects with acne on the chest and/or back, weigh and dispense 4 bottles or 2 tubes of study product. The tear-off panel is to be affixed to the source document and filed in subject's chart. Instruct subject on study product use. Review the Subject Instructions with subject. Instruct subject to not discuss study product with Investigator or other study staff.
  - c) Supervise the first application of study product at the site to ensure that it is done correctly.
  - d) Remind subject to bring all bottles or tubes of study product to next visit.
  - e) Dispense and review use of diary. Remind subject to report missed applications and/or potential AEs as well as any medication used in the diary and to bring diary to each visit.
- 10. Schedule next visit.
- 11. Complete eCRF for randomized subjects. For every screen failure subject, record the subject number, date of visit, date of consent, reason for screen failure, and study status (screen failure) in the eCRF.

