## 7.10.3 Visit 3 – Week 4/Day 28 (Visit Window $\pm$ 3 Days)

- 1. Evaluate treatment and protocol compliance and record any deviations. This includes a review of the diary card for number of applications and missed applications.
- 2. Conduct clinical assessments:
  - a. IGA for the face (Table 4). IGA assessments should always be done prior to lesion counts.
  - b. Count inflammatory and non-inflammatory lesions on face and, if applicable, on chest

- and/or back (including shoulders) for selected site(s). These counts should be recorded separately for the face and, if applicable, chest and/or back (including shoulders) for selected site(s).
- c. Local cutaneous safety evaluation for dryness, non-lesional erythema, and peeling. The investigator should also ask the subject if any burning, stinging, or itching has occurred on the face since the last visit. These evaluations should be recorded separately for the face and, if applicable, chest and/or back (including shoulders) for selected site(s).
- 3. Administer the CADI questionnaire.
- 4. Collect vital signs (blood pressure and pulse).
- 5. Conduct a urine pregnancy test for all females.
- 6. Collect AE data. This includes a review of the diary card for potential AEs.
- 7. Update concomitant medications data.
- 8. The independent third party study medication dispenser will perform the following procedures:
  - a) Dispense diary and review instructions. Remind subject to bring all bottles or tubes of study product to each visit.
  - b) Weigh and then dispense study product, 1 new bottle or 1 new tube, and collect used bottles or tubes. For the selected site(s) who will enroll subjects with acne on the chest and/or back, weigh and dispense, or 3 bottles or 2 tubes of study product. Weigh bottles or tubes when they are collected. Redispense old bottles/tubes as needed. Instruct subject to not discuss study product with Investigator or other study staff.
- 9. Schedule next visit.
- 10. Complete eCRF.

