# APPENDIX 2: THE CARDIFF ACNE DISABILITY INDEX (CADI)

1. As a result of having acne, during the last month have you been aggressive, frustrated or embarrassed?	

(a) Very much indeed

(b) A lot

(c) A little

(d) Not at all

2. Do you think that having acne during the last month interfered with your daily social life, social events or relationships with members of the opposite sex?	

(a) Severely, affecting all activities

(b) Moderately, in most activities

(c) Occasionally or in only some activities

(d) Not at all

3. During the last month have you avoided public changing facilities or wearing swimming costumes because of your acne?	

(a) All of the time

(b) Most of the time

(c) Occasionally

(d) Not at all

4. How would you describe your feelings about the appearance of your skin over the last month?	

(a) Very depressed and miserable

(b) Usually concerned

(c) Occasionally concerned

(d) Not bothered

5. Please indicate how bad you think your acne is now:	

(a) The worst it could possibly be

(b) A major problem

(c) A minor problem

(d) Not a problem

© Cardiff Acne Disability Index. R J Motley, A Y Finlay 1992

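### At Visits 2 to 5 the visit lists place CADI directly after the investigator's examination and irritation questions, and no rule requires the subject to complete it first

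*Protocol*

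**What the plan says.** The protocol synopsis (Methods) introduces the questionnaire with "The Cardiff Acne Disability Index (CADI) will be used to assess the quality of life in all subjects at Baseline (Day 1", and goes on to name Weeks 4, 8 and 12. Protocol Section 7.5.4 says: "The CADI is a short 5 item questionnaire that will be conducted by all subjects at Baseline, Week 4, 8, and 12". Neither that section nor SAP Section 8.1.4 says at what point in the visit the subject should answer.

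The visit lists do show a position. At Baseline (Section 7.10.2), item 7 is the clinical assessments and the next line is "8. Administer the CADI questionnaire". At Weeks 4, 8 and 12 (Sections 7.10.3 to 7.10.5), item 2 is the clinical assessments and the next line is "3. Administer the CADI questionnaire". Each block of clinical assessments contains the IGA, the lesion counts and the grading of dryness, erythema and peeling. It closes with questions to the subject, worded after Baseline as "The investigator should also ask the subject if any burning, stinging, or itching has occurred on the face since the last visit".

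One order rule is stated among the efficacy assessments, in Section 7.5.1 and repeated in the visit lists: "The IGA should always be done prior to lesion counts".

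CADI is the only patient-reported variable among the efficacy endpoints (Protocol Section 11.4; SAP Sections 3.2.2 and 8.3). Stinging, burning and itching are also reported by the subject, but they are safety endpoints.

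**The concern.** CADI is there to record the subject's own view, apart from the investigator's grade and counts. The protocol accepts that the order of assessments can influence a rating, since it fixes the IGA ahead of the counts. It gives the subject's rating no similar protection.

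The examination is hard for the subject to ignore. Subjects aged 12 and over need at least 20 inflammatory and 25 non-inflammatory facial lesions at Baseline, so at least 20 + 25 = 45 lesions are counted, and the skin may be stretched to see closed comedones (Section 7.5.2). The subject is then asked about irritation. If the list is followed, the next thing put to the subject includes "Please indicate how bad you think your acne is now".

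At stake is whether the CADI summaries reflect the subject's independent view, and whether the answers could be primed differently in the lotion and cream arms.

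**Working it through.** Neither document gives a figure for this point. The check compares sections and adds some scale arithmetic.

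**1. Position in each list (Protocol Sections 7.10.1 to 7.10.5).**

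| Visit | Investigator's assessments | CADI |
|---|---|---|
| 1, Screening | items 6 and 7 (IGA, facial counts) | not given |
| 2, Baseline | item 7 | item 8 |
| 3, Week 4 | item 2 | item 3 |
| 4, Week 8 | item 2 | item 3 |
| 5, Week 12 | item 2 (adds overall tolerance) | item 3 |

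CADI follows the examination in 4 of the 4 lists that contain it. Protocol Table 1 and SAP Table 2 show their rows in the same order, but a visit grid does not set the order within a visit, so I give that no weight.

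**2. Is the list a time sequence?** Neither document says so, and the Baseline list cannot be a strict one. Eligibility is confirmed at item 3, ahead of the pregnancy test (4), physical examination (5), vital signs (6) and IGA and counts (7) on which it depends. Elsewhere, timing that matters is put in words: IGA before counts, skin type before the first application (Section 7.4), Visit 2 tolerance before the first application (Section 7.6). For CADI there are no such words. The list suggests an order without requiring it.

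**3. Which items are exposed?** In Appendix 2, items 1 to 4 ask about the last month. Only item 5 asks about the present. An immediate effect of the examination is most plausible for 1 item of 5.

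**4. Scale.** Five items scored 0 to 3 give a maximum of 5 × 3 = 15.
- One category on item 5: 1/15 = 6.7% of the range.
- One category on each of items 4 and 5: 2/15 = 13.3%. This treats item 4 like item 5 despite its one-month recall.

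These are assumed steps in one subject's raw score, not estimates of an order effect.

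**5. What reaches the endpoint.** Let d_B be the mean shift caused by the order at Baseline and d_t the mean shift at a later visit.
- Observed change = true change + (d_t − d_B). If d_t = d_B, the extra term is zero.
- Lotion (L) against cream (C): extra term = (d_t,L − d_B,L) − (d_t,C − d_B,C). Baseline CADI (item 8) is listed before randomization (item 9), so for subjects randomized across all four arms d_B should be equal on average. What remains is d_t,L − d_t,C.

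**6. Could d_t differ by arm?** The irritation questions come just before CADI, and after Baseline the answers to them depend on treatment. Section 8 reports desquamation, dry skin, erythema and burning in 10% to 30% of subjects on tazarotene cream 0.1%, and pruritus and stinging in 1% to 5%. Subjects also know whether they use lotion or cream (Section 6.5.1).

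As an illustration only, borrow that 10% to 30%. Assume that this share of one arm moves item 5 by one category because of the exchange, and nobody in the other arm does. The arm means then differ by 0.10 × 1 = 0.1 to 0.30 × 1 = 0.3 points, or 0.1/15 = 0.7% to 0.3/15 = 2.0% of the range. Neither the size nor the direction of a real effect can be derived from the documents.

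**The case against.** The strongest reply is that this is a convention about questionnaires, not a contradiction in the plan. A reader might infer that CADI is in fact answered under the influence of the examination at every visit. The documents do not support that. The list is not binding, a site could give CADI first without breaking any rule, Screening has no CADI, and nothing says that subjects are told their grade or counts.

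A reader might also infer that agreement between CADI change and lesion change would be partly produced by the procedure. No analysis of such agreement is planned; CADI receives only descriptive summaries of change from baseline (Protocol Section 11.4; SAP Section 8.3). The listed order is also the same in every arm and at every CADI visit, so a constant shift would largely cancel.

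All of that stands, and it keeps the point small. It does not remove it. Silence on timing, together with a written order that puts the questionnaire second, leaves the matter to each of 10 centers. The cancellation argument covers only a constant shift, and the irritation questions need not produce one.

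A practical objection also stands. When Visits 1 and 2 are combined, the IGA and counts appear among the Visit 1 items as well, so moving the line in the later lists alone would not put CADI first.

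**Conclusion.** The point holds as a possible priming influence that the protocol does not prevent. It is not a demonstrated bias. At the four CADI visits the only written position is directly after the examination, and no sentence requires the reverse. Item 5 is the most exposed.

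The consequence is limited: CADI is a secondary endpoint, summarized descriptively, in a study that is not powered and whose objectives are safety and local tolerability. The documents give no size for an order effect. The figures under the working rest on assumed category shifts and show scale only. Any effect on the comparison of arms requires sites to have followed the list and the later shift to differ between lotion and cream; neither can be confirmed from the documents. This is a cheap improvement, not a defect that threatens a planned result.

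**What to change.** In Protocol Section 7.5.4 and in the lists in Sections 7.10.2 to 7.10.5, state that the subject completes the CADI before the IGA, lesion counts, tolerance grading and symptom questions at that visit, and move the line up accordingly. Add that when Visits 1 and 2 are combined, CADI comes after consent and before the Visit 1 IGA and counts.

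The cost is one sentence and one moved line in four lists, plus the note on combined visits. No visit, variable or analysis is added. The downside is that some subjects will complete a CADI form and then fail Baseline eligibility. Section 7.10.2 asks for only a few identifying and status fields in the eCRF for screen failures, so those forms need not be entered.

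The SAP describes the study largely in the past tense. If the visits are already done, the clinical study report should state the order used, or that it was not recorded, as a limitation of the CADI results.

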## **Number of Subjects:**

Approximately 150 subjects with facial acne vulgaris will be randomized at 10 centers to have 120 subjects who complete the study.

# **Diagnosis and Criteria for Inclusion / Exclusion:**

### **Inclusion:**

- 1. Subject understands the study procedures, is willing to comply with the study procedures and required visits, and agrees to participate by giving written informed consent. Subjects under the legal age of consent must provide written assent and must have the written informed consent of their legal guardian.
- 2. Subject (or legal guardian) must be willing to authorize use and disclosure of protected health information collected for the study.
- 3. Subject must be at least 12 years of age.
  - At selected site(s), a total of approximately eight subjects 9-11 years of age will be enrolled into the 2 arms of DFD-03 lotion group (active and vehicle).
- 4. Female subjects must be having their menstrual period at the Baseline Visit (as reported by the subject), except for subjects using hormonal contraceptives that preclude menstrual periods, if the subject is premenarchal, is postmenopausal for at least 12 months prior to baseline, is surgically sterilized (i.e. tubal ligation) or if the subject is without a uterus and /or both ovaries.
- 5. A clinical diagnosis of facial acne vulgaris with a facial Investigator's Global Assessment (IGA) score of 2 (mild) to 3 (moderate) at Baseline.
  - At selected site(s), up to twelve subjects with acne lesions on the chest and/or back (including shoulders) in addition to those on the face will treat their back and/or chest (including shoulders) in addition to their face.
- 6. Inflammatory lesion count (papules and pustules) of at least 20 on the face, including the nose, at Baseline.

- This criteria is not applicable to the 9-11 years age group as long as subjects have an IGA score of 2 (mild) to 3 (moderate) at Baseline.
- 7. Non-inflammatory lesion count (closed and open comedones) of at least 25 on the face, including the nose, at Baseline.
  - This criteria is not applicable to the 9-11 years age group as long as subjects have an IGA score of 2 (mild) to 3 (moderate) at Baseline..
- 8. No more than 2 nodulocystic lesions on the face, including the nose, at Baseline.
- 9. Females, regardless of childbearing potential:
  - a. Must have a negative urine pregnancy test at Screening and Baseline. Test must have a sensitivity of at least 25 mIU/mL for βhCG.
  - b. If sexually active, must be on or use an acceptable method of birth control.

## Acceptable methods of birth control include:

- hormonal methods\* or intrauterine device in use  $\geq 90$  days prior to Baseline; or
- partner has had a vasectomy at least 90 days prior to Baseline; or
- barrier methods plus spermicide; or
- Essure® that has been in place for at least 3 months before the screening visit with radiograph confirmation of fallopian tube blockage.

\*Hormonal methods: If on hormonal contraceptives, must have been on the same hormonal contraceptive product for 3 months (90 days) prior to Baseline and continued on same method and dose throughout the duration of the study. If subject had used hormonal birth control and had stopped, this should have occurred more than 6 months prior to Baseline.

**Exception:** Sexually inactive female subjects are not required to practice a reliable method of contraception and may be enrolled at the investigator's discretion provided that they are counseled to remain sexually inactive for the duration of the study and understand the possible risks involved in getting pregnant during the study. An abstinent female must agree that if she becomes sexually active during the study she will use an acceptable form of contraception such as a barrier method with spermicide. Females who are surgically sterilized [e.g. hysterectomy, bilateral tubal ligation, bilateral oophorectomy] at least 1 year prior to Baseline or have been postmenopausal for at least 1 year prior to Baseline are not required to practice a reliable method of contraception.

- 10. Subjects agree not to use any product on the face during the entire course of study except for non-medicated, investigator-approved cleanser, sunscreen, face wash, and make-up. Subjects should continue to use these investigator-approved products for the duration of the study and should avoid any changes in these consumer products.
- 11. Subjects must be willing to comply with sun avoidance measures for the face (as well as back/chest including shoulders, if applicable) including use of investigator-approved sunscreen and/or hats, have limited sun exposure time, and have no tanning bed use.

- 12. Subject must be in good general health as determined by the investigator and supported by the medical history, physical examination, and normal or not clinically significant abnormal vital signs (blood pressure and pulse). Subjects are eligible if:
  - Systolic blood pressure (BP) < 160 and > 85 mmHg
  - Diastolic BP < 100 and > 50 mmHg
  - Pulse 50 to 100 bpm inclusive for adults; up to 110 bpm for subjects < 18 years of age

